Harp's pharmacists will screen patients in their MTM program and enroll them in familial or peer clusters consisting of 1 or more subjects and randomize them into 1 of the 4 study arms using a site specific randomization schedule. Each arm will receive pre and post testing and health literacy evaluation. Two education arms will use the 139 page CKD: What You Need to Know workbook including the CKD Action Plan as self-study tools and follow-up during regular MTM appointment. The 3 arms include 2 education arms and a control arm with various levels of intervention: Arm 1) case management model including pharmacist initiated discussion of workbook content and action plan reinforcement, Arm 2) brief introduction of the workbook and action plan reinforcement, Arm and Arm 3) the control group will receive a list of web-based CKD sites and a copy of the action plan with no additional intervention. Patient initiated CKD discussions will be tracked by both the pharmacist and staff by topic and time spent. Time spent by the pharmacist and staff will be calculated along with outcomes and compared in each group. Data collected upon enrollment will include year of birth, race, gender, county of residence, history of CKD, diabetes, hypertension and/or heart failure, patient reported blood pressure, AIC, eGFR and hemoglobin, smoking history, renal transplant history and if is under the care of or has been seen by a nephrologist in the past.

The CKD: What You Need to Know Workbook is 139 pages and includes:

- An Introduction
- 8 Chapters plus resources:
 1. Kidneys and Chronic Kidney Disease (CKD)
 2. Protecting Your kidneys and Slowing CKD Progression
 3. Your Choices for Dialysis and Transplantation
 4. Lab Results: What they mean & What you can control
 5. Chronic Kidney Disease & Eating Habits

6. Chronic Kidney Disease & Meds
7. Learning to Cope with Kidney Disease
8. Paying for Your CKD Treatment
9. CKD Action Plan
10. Web-based Resources
11. Kidney Talk: What do these words mean?
12. Resources

Each section ends with “Frequently Asked Questions”, “Test Your Knowledge” and has space for notes. Patient testimonies are found at the back of 6 chapters.

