Know workbook, slide sets, CKD action plan, Label reading exercise, Web-based resource list, data collection sheets, pre and post tests and program evaluation. UAMS staff will participate in the initial education of Harps staff and future education, as requested. UAMS will make the 10 points of CKD Care for Primary Care Providers (PCPs) available to both Harps staff and local PCPs, as requested.

Harps oversight staff and UAMS research staff will have monthly web-based or face to face meetings, with additional communication as needed.

Reporting requirements are the same for each site and outlined in the data section above. A central site may be selected by Harps when the sites are selected and serve as a model or mentoring site.

Data Analysis

Study arms will be compared by RRT choice using logistic regression that includes covariates found to differ between the groups. Results will be reported in terms of odds ratios and their 95% confidence intervals. Each group will be compared on the ability to choose a modality by the end of their 2nd or 3rd MTM visit, depending on their study arm and at the end of the study (June 2022) by comparing pre and post testing and program evaluation answers. To ensure balance in patient characteristics across clusters chi-square or Fisher's exact test, as appropriate, will be used to evaluate categorical measures, whereas two-sample t-test or Wilcoxon rank test, as appropriate, will be used for continuous measures.

The primary study aim is the ability of the participants to choose a dialysis modality by the end of their second or third visit, depending on their study arm. Descriptive statistics will be used to examine the trend in the patients' ability to choose a dialysis modality, level of interest in kidney transplant, the selection of a possible donor and having enough information to decide across the two assessment periods.

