Secondary outcomes will be compared in all clusters. Because randomization seldom results in samples that are balanced on all baseline characteristics, information on control variables relevant to choice of dialysis mode will be collected, including age, gender, baseline intent to start home based dialysis, whether currently being followed by a nephrologist, patient engagement measured by the percent of visits where CKD patient initiated discussion took place and self-reported and provider confirmed outcomes listed in study plan. Pharmacists and staff time will be compared between arms and linked to costs to support each intervention arm. Tests appropriate for the measure will be used when comparing baseline characteristics between the research arms.

The sample size was based on what was appropriate for what could be reasonably be accomplished in the time frame with the available funding. Power based on the primary aim was a secondary consideration. A population of 100 clusters could result in a much larger population of subjects depending on the size of the clusters. Utilizing clusters to essentially train peer educators and describe their training methods, as well as, the outcomes of each of their cluster members can inform future research involving CKD peer educator led CKD patient education programs.

Ethical Considerations

This study will be conducted in accordance with all applicable government regulations and University of Arkansas for Medical Sciences research policies and procedures. This protocol and any amendments will be submitted and approved by the UAMS Institutional Review Board (IRB) to conduct the study.

This study meets the criteria for exempt review and does not require formal consent of the subjects. However, a Patient Information Sheet explaining the study will be provided to interested parties. After discussion with Harp's pharmacist, verbal consent will be obtained and completion of the pre-test will be evidence of consent. UAMS will receive no HIPAA data on subjects. All data will be de-identified as outlined above and a HIPPA waiver has been requested.

Dissemination of Data

Results of this study may be used for presentations, posters, or publications. The publications will not contain any identifiable information that could be linked to a participant.

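### The primary logistic model takes its covariates from whatever is found to differ between arms, so chance imbalance, not prognosis, decides which odds ratio is reported

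*Combined protocol and SAP*

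**What the plan says.** All analysis text is in the Data Analysis section of the combined protocol and SAP.

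- **Primary model.** The arms are compared by "logistic regression that includes covariates found to differ between the groups", reported as odds ratios with 95% confidence intervals.
- **How differences are looked for.** Categorical measures get a chi-square or Fisher's exact test. For continuous measures a "two-sample t-test or Wilcoxon rank test, as appropriate, will be used for continuous measures". A later paragraph adds: "Tests appropriate for the measure will be used when comparing baseline characteristics between the research arms". No significance level or standardised-difference cut-off is given. It is not said whether a difference is judged across all arms or pair by pair.
- **Control variables.** The same later paragraph says that "information on control variables relevant to choice of dialysis mode will be collected". Its open list names age, gender, baseline intent for home dialysis, nephrologist follow-up, "patient engagement measured by the percent of visits where CKD patient initiated discussion took place", and the outcomes in the study plan. It does not say which of these enter the primary model.
- **Candidate pool.** Study Design and Procedures states: "Data collected upon enrollment will include year of birth, race, gender, county of residence, history of CKD, diabetes, hypertension and/or heart failure". It continues with "patient reported blood pressure, AIC, eGFR and hemoglobin, smoking history, renal transplant history" and with nephrologist care.
- **Design.** The visit table shows two education arms and a control. A total of 100 family or peer clusters are to be randomised on site-specific schedules.

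**The concern.** In a randomised trial an observed baseline difference is a chance event. It does not show that the variable predicts the outcome. A rule that adjusts for what differs can therefore bring in variables that do not matter and leave out the one that does. Here that is probably baseline intent, the listed variable closest to the outcome.

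The odds ratio also depends on which prognostic variables are in the model, even when they are perfectly balanced. Two analysts who follow the text with different cut-offs could properly report odds ratios with different meanings. The reader cannot know beforehand which one will be reported.

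Engagement raises a different issue. It can be known only once visits have taken place, and the arms differ in who starts the conversation: Arm 1 is a "case management model including pharmacist initiated discussion of workbook content and action plan reinforcement", while control visits only answer the patient's questions. If engagement were adjusted for and the arm affected it, the odds ratio would no longer be the total effect of the arm.

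**Working it through.** The plan gives no power, effect size, threshold, intraclass correlation or baseline intent rate, so there is no figure of its own to reproduce. Every input below that is not a count from the documents is an assumption.

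**1. How often chance picks a covariate.** Enrollment data comprise 15 variables: birth year, race, gender, county, four disease histories, blood pressure, A1C, eGFR, hemoglobin, smoking, transplant history and nephrologist care. Baseline intent makes 16. If they are independent, P(at least one flagged) = 1 − (1 − a)^16.

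- a = 0.05: 1 − 0.95^16 = 56%, expected number 16 × 0.05 = 0.8.
- a = 0.20: 1 − 0.80^16 = 97%, expected number 16 × 0.20 = 3.2.

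The variables are in fact linked (diabetes with A1C, CKD with eGFR), so these figures are too high. With a common correlation of 0.3 or 0.5 between normal test statistics, numerical integration gives about 48% or 37% at the 5% threshold.

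**2. How often baseline intent is selected.** This was simulated with 5,000 runs, 33/33/34 clusters, clusters of one, of one to three, or of two, and overall or any-pair tests.

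| Threshold | Intent 3% | Intent 10–50% |
|---|---|---|
| 5% | left out in 90–99.7% of trials | left out in 76–96% |
| 20% | selected in 8–35% | selected in 21–55% |

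**3. What leaving it out does to the odds ratio.** Assume intercept −1.5, arm log-OR 1.3 (OR 3.67) and intent log-OR g with prevalence q. Let expit(x) = 1/(1 + e^−x). The choice rates are then:

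- control = (1 − q)·expit(−1.5) + q·expit(−1.5 + g)
- arm = (1 − q)·expit(−0.2) + q·expit(−0.2 + g)

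For q = 0.10 and g = 1.5:

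- control = 0.9 × 0.1824 + 0.1 × 0.5000 = 0.2142
- arm = 0.9 × 0.4502 + 0.1 × 0.7858 = 0.4837
- OR = (0.4837/0.5163)/(0.2142/0.7858) = 3.44

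| Intent prevalence | OR without intent, g = 1.5 | g = 2.5 |
|---|---|---|
| 3% | 3.59 | 3.49 |
| 10% | 3.44 | 3.16 |
| 30% | 3.19 | 2.68 |

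For scale, take 33 v 34 single-person clusters. In the worked case SE = √[1/(33 × 0.2142 × 0.7858) + 1/(34 × 0.4837 × 0.5163)] = 0.546. The shift is ln(3.67/3.44) = 0.065, or 0.12 SE. The 95% interval around 3.44 is exp(1.235 ± 1.96 × 0.546) = 1.18 to 10.0.

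**4. Power and type I error.** These were simulated with 2,000 runs, 33 v 34 clusters and cluster-robust Wald tests. Power is shown for the 5% rule v always adjusting for intent; the Monte Carlo SE is about 1.1 points per figure.

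| Intent | Single-person, g = 1.5 | Single-person, g = 2.5 | Clusters of 1–3, g = 1.5 | Clusters of 1–3, g = 2.5 |
|---|---|---|---|---|
| 3% | .632 v .636 | .612 v .620 | .683 v .690 | .668 v .676 |
| 10% | .632 v .642 | .604 v .623 | .670 v .689 | .653 v .676 |
| 30% | .620 v .627 | .524 v .576 | .663 v .707 | .585 v .657 |

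Rejection under the null was 2.5–5.6%, so selection does not inflate type I error.

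**5. Engagement, if it were to enter.** Assume intercept −2.0, a direct arm log-OR of 0.6, engagement log-OR 2.0 over three visits, single-person clusters, and entry when a Wilcoxon test gives p < 0.05.

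- Engagement 30% in control, 60% in the arm: total OR 3.12, estimated at 1.84.
- Engagement 60% in control, 30% in the arm: total OR 0.99, estimated at 1.86.
- With log-OR 1.0 and 30% in both: total OR 1.81, median estimate 1.85 with or without the rule, so no bias from adjustment.

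The direction depends on how the arm changes patient-initiated talk, and the documents do not say.

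**The case against.** The strongest reply is that little is lost. This is a pilot sized on time and funding, with power a secondary consideration. Type I error is safe. The shift in the odds ratio at 3–10% intent is 0.04 to 0.28 of a standard error, and it comes from non-collapsibility: a different valid odds ratio, not a biased one. All of this stands and limits the weight of the point. It does not defend the rule, because the plan still specifies arm comparisons with odds ratios and 95% intervals, and a fixed list costs nothing extra.

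Three stronger readings are tempting, and the documents do not support them.

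- **That engagement is planned as a primary-model covariate.** The sentence is motivated by baseline imbalance, speaks of collecting information, and is followed by tests of baseline characteristics. No text puts engagement in the model. What remains is that no text excludes it, and that calling it a control variable relevant to dialysis choice makes adjustment a plausible reading. The outcomes on the same list have enrollment values, so only their follow-up values raise the issue.
- **That engagement would mask a benefit.** The measure counts discussions that patients start. Pharmacist-led talk in Arm 1 could lower it as easily as raise it, and Arm 2 and control both provide for answering questions at Visits 2 and 3.
- **That the balance tests cannot handle three arms.** Only the t-test and Wilcoxon wording is two-sample. Chi-square and Fisher's tests cover three arms, and the later paragraph allows any suitable test.

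**Conclusion.** The point holds as a flaw in how the primary model is specified, and it should be corrected. Followed as written, the rule lets chance imbalance choose the model, and at a 5% threshold it would usually leave out baseline intent. The cost is an odds ratio that is not fixed before the data are seen, plus a power loss of about 0–2 points at 3–10% intent and up to about 7 points at 30%. A reader might infer a raised false-positive rate; the null simulations show none for baseline covariates.

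These sizes rest on assumed intent rates, effect sizes and cluster sizes. The nearest figures in the documents, under 3% to 11%, are rates of incident home dialysis use, not of stated intent. The 56% and 97% are upper-end figures because they assume independence.

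Engagement is a secondary point of wording. If it entered and the arm affected it, the total effect would no longer be estimated, with size and direction not determinable from the documents.

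**What to change.** Replace the rule in Data Analysis with the following.

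1. **Fixed covariates, included whatever the observed balance:** arm and the pre-test modality choice, or baseline intent if the pre-test lacks that item. Add age, gender and nephrologist follow-up only if the number of events allows, by a criterion written down beforehand.
2. **One named model:** logistic GEE clustered on the randomised family or peer cluster, with a small-sample variance correction. This fixes one odds ratio, averaged over clusters and given the listed covariates. A random-intercept model would estimate a different one, so the two should not be offered as alternatives. The cluster term answers a separate defect and is not counted as a benefit here.
3. **Site:** add it if the number of sites allows, because the schedules are site specific, with the pooling rule for small sites set before data are seen.
4. **Exclusions:** engagement and follow-up values of the visit outcomes do not enter the primary model. Report them descriptively or in a secondary analysis.
5. **Baseline table:** describe characteristics by arm, and do not use it to choose covariates.

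The cost is SAP wording. The pre-test is done at Visit 1, and the study number already carries site and cluster. The pre-test items are not shown, so the matching item must be confirmed. The drawbacks are a few degrees of freedom, possibly sparse cells, and little power gain if baseline intent is rare; the benefit is then mainly a model fixed in advance.

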Harp's Pharmacy has a successful medication therapy management (MTM) program where pharmacists are provided time for patient-centered activities for patients with diabetes (DM), hypertension (HTN), the 2 leading causes for CKD, and heart failure (HF), the leading cause of death in CKD. Thirty six percent of patients with DM will develop CKD and hypertension can be both a cause and an effect of CKD (5). In this project they will use their MTM infrastructure to add CKD to their program in select pharmacies in the delta. The CKD tools build on and support actions that improve the underlying conditions that are already being addressed. The "CKD: What Your Need to Know" tools will be used with patients with known CKD or 2 of the 3 conditions covered by MTM and randomized into 1 of 3 education arms that offer various levels of support or a control arm.

Using non-nephrology clinicians to expand access to education earlier in their disease progress is essential. This project will inform how various levels of support provided by pharmacists and their staff using nephrology developed tools can effect patient choice allowing comparisons of support time and outcomes. Empowering patients to be proactive partners in their health care, through education and accountability, by choosing both their RRT and performance goals to protect their kidneys is key to improving outcomes. Demonstrating that non-nephrology clinicians can effectively educate and support these patients will provide models that other clinicians can use.

Minorities, especially in rural areas, are less likely to receive most kinds of care including evidence-based practices, home dialysis or transplantation (4,5). Developing patient-centered approaches to care such as this project can reduce disparities.

One-on-one outreach to educate and motivate patients and seek their feedback can strengthen commitment and adherence to medical regimens. Learning what to expect can promote self-management behaviors.

The AR Department of Health (ADH) Southeast (SE) region covers most of the Delta and was selected because it has the poorest outcomes for patients starting RRT. In 2017, new patients were predominately black (61%), less than half had seen a nephrologist prior to starting RRT, only 1.3% had seen a dietitian, most (92.3%) started hemodialysis using a catheter and 2.1% started on home peritoneal dialysis. Only 2.1% had no insurance (9). This data can be tracked annually to track impact.

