The workbook went through health literacy editing with a goal of a 5th grade reading level. The chapters ranged from 3rd to 7th grade levels. It was felt that it was important for subjects to learn or at least be exposed to words that were kidney related and frequently used by their health care providers. So the first time each of these words were used in the workbook they were red and the definition was in the kidney talk section on that page. Then the first time the word appeared in subsequent chapters the word was in red but no definition was on that page.

Subjects will be randomized into 1 of 2 education arms that offer various levels of support or a control arm using a site specific computer generated randomization schedule. Presumed monthly visits.

Study Arm	Handouts	Visit 1*	Visit 2	Visit 3	End of Study June 2022
Testing		Pre-test		Post-Test	Evaluation
1: Case Study Model	Workbook Action Plan (V1) Label reading Exercise (V2)	Pharmacist initiated review of workbook and assist with Action Plan goal selection	Action Plan Reinforcement. Discuss Chapters 1-4. Provide “Label Reading Exercise”	Action Plan Reinforcement. Discuss Chapters 5-8 and resources. Review results of Label exercise	Open conversations from each party for all arms after evaluation
2: Minimal Instruction	Workbook Action Plan	Briefly explain handouts with focus on Action Plan.(5-10 minutes)	Action Plan Reinforcement. Answer patient’s questions.	Action Plan Reinforcement. Answer patient’s questions.	As Above
3: Control	Resource List Action Plan	Answer patient’s questions.	Answer patient’s questions.	Answer patient’s questions.	As Above

*On first visit, education arms subjects will be asked to read 1 chapter of the workbook weekly. All subjects will receive a CKD Action Plan and be asked to set individual goals.

Secondary outcome data collected at each visit include both self-reported and/or

Title: Pragmatic Approach to Chronic Kidney Disease Education in the Delta V.6

PI: [name]

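### The balance check for continuous measures is a two-group test in a three-arm trial and feeds the choice of primary-model covariates; separately, the primary regression names no joint arm test or contrasts

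*Combined protocol and SAP*

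**What the plan says.** **Arms.** Study Design and Procedures states: "Subjects will be randomized into 1 of 2 education arms that offer various levels of support or a control arm". The list of arms agrees: "The 3 arms include 2 education arms and a control arm with various levels of intervention". The same section also says clusters will be assigned differently: "randomize them into 1 of the 4 study arms using a site specific randomization schedule". The background text before Specific Aims has subjects "randomized into 1 of 3 education arms that offer various levels of support or a control arm", which also makes four.

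**Balance check.** Data Analysis introduces a set of tests whose stated purpose is balance in patient characteristics across clusters. Categorical measures get chi-square or Fisher's exact test. For the rest, "two-sample t-test or Wilcoxon rank test, as appropriate, will be used for continuous measures". Later in the section, baseline characteristics are to be compared between the research arms with tests suited to the measure.

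**Primary analysis.** "Study arms will be compared by RRT choice using logistic regression that includes covariates found to differ between the groups". Results are odds ratios with 95% confidence intervals. The outcome is binary: "The primary study aim is the ability of the participants to choose a dialysis modality by the end of their second or third visit". The groups are also compared in June 2022, and the trend across the two assessment periods is to be examined with descriptive statistics.

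**Not stated anywhere:** a joint test of arm, a reference arm, a list of contrasts, a significance level, a multiplicity rule, or a cluster term in the model.

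**The concern.** There are two separate matters.

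**1. The balance test does not fit the design.** Chi-square and Fisher's test extend to three arms. The two-sample t-test and the Wilcoxon rank test do not, so for continuous measures the sentence cannot be carried out as one test per measure. The natural workaround is three pairwise tests. The result is not merely a table footnote: a measure that is found to differ becomes a covariate in the primary model. The content of that model would therefore depend on a procedure that is not defined for this trial and that flags chance differences too often. Under randomisation such differences are chance in any case.

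**2. The primary comparison is left open.** A three-level arm variable gives two odds ratios against a reference and a third by changing the reference. With no contrasts named and no overall test first, any interval that excludes 1 could be put forward as evidence that one level of support works. The 95% intervals do not allow for that choice.

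**Working it through.** The plan states no significance level, power or family-wise error rate, so there is no planned figure to reproduce.

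**Inputs**
- Three arms (Study Design and Procedures); 100 clusters of one or more people (Study Population).
- Equal allocation, about 33/33/34: an assumption, as no ratio is stated.
- Each test at two-sided 0.05, critical value 1.96: inferred from the 95% intervals.
- Independent subjects: an assumption, relaxed below.

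**Point 1: three pairwise tests on one baseline measure**
1. With equal standard errors, some pair has |z| > 1.96 exactly when the range of the three standardised arm means exceeds 1.96 × √2 = 2.77.
2. The studentised-range tail for three groups at 2.77 (large samples) is 0.122, so a measure is flagged by chance 12.2% of the time. Simulated pairwise t-tests and Wilcoxon tests at 33/33/34 also give about 12%. One three-arm test (F-test or Kruskal-Wallis) gives about 5%.
3. Illustration: the enrolment data list year of birth, blood pressure, A1C, eGFR and hemoglobin. Counting blood pressure once, that is five continuous measures. Expected number flagged by chance: 5 × 0.122 = 0.61 with pairwise tests, against 5 × 0.05 = 0.25 with one test each.

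**Point 2: primary odds ratios, equal true rates in all arms**

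| What is read at 0.05 | At least one false positive | With joint 2-df test required first |
|---|---|---|
| Two education arms against control | 9.1% | 4.2% |
| All three pairs | 12.2% | 5.0% |

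These are large-sample values. With 33/33/34 single-person clusters, Wald tests and assumed choice rates of 30–70%, the ungated figures are 8.3–9.1% and 11.3–11.7%.

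**Why the joint test is enough with three arms.** If all arms are equal, the joint test holds the error at 5%. If exactly one pair is equal, only one true null remains and it is tested at 0.05. No further correction is needed.

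**Why the arm count matters.** With four arms, the ungated figures are 12.5% (three against control) and 20.3% (six pairs). The argument above also fails: one arm could differ, pass the joint test, and leave three equal arms with the 12.2% of step 2.

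**Why clusters matter.** Cluster sizes and correlation are not given, so these are assumed values. Design effect DE = 1 + (m − 1) × ICC. If clustering is ignored, the joint test rejects a true null with probability exp(−5.991 / (2 × DE)):
- m = 2, ICC 0.1: DE 1.1, 6.6%
- m = 3, ICC 0.1: DE 1.2, 8.2%
- m = 3, ICC 0.3: DE 1.6, about 15%

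Over sizes 2–3 and ICC 0.1–0.3, ungated reading with clustering ignored gives about 11–21% for two contrasts and 14–27% for three pairs.

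**Cost of the joint test.** At assumed true rates of 30/45/60% with 33 independent subjects per arm, the chance of at least one significant pair falls from 73% to about 60–61%.

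**The case against.** The strongest objections concern how far the two points can be pushed.

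- **A reader might infer that the two-sample tests inflate the primary error rate to 12%.** They do not. That sentence concerns balance of patient characteristics, while the primary outcome is binary and goes to logistic regression. The only link is through which covariates enter the model. This objection stands, and the points are kept apart for that reason.
- **A reader might infer that the plan commits to three separate odds-ratio tests.** It does not. It says "Study arms will be compared by RRT choice using logistic regression" and stops there; such a model permits a joint test. Reading only the two contrasts against control gives about 9%, so 12% is the upper end of a range and not a property of the plan. The project does aim to compare levels of support, so the contrast between the two education arms is plausibly in scope.
- **A reader might count June 2022 as a second confirmatory test.** The documents do not support this. The primary aim is fixed at the second or third visit, and the trend across periods is descriptive. Because another sentence does compare groups in June 2022, a label is still useful.
- **The later sentence on suitable tests between arms partly repairs the balance check.** It suggests that the word clusters is loose. It does not replace the only tests named for continuous measures.
- **This is a pilot, sized on time and funding, that reports estimates.** Strict family-wise control therefore matters less, which is why the second point is the smaller one. The stated hope of providing models for other clinicians still makes it worth naming the contrasts in advance.

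**Conclusion.** The first point holds: the balance check is wrong as written. It names a two-group test for a three-arm design, refers to clusters where the randomised comparison is between arms, and helps to decide the primary model. Done pairwise, it flags a measure by chance about 12% of the time instead of 5%.

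The second point holds as a gap in specification, not as an error built into the plan. If each odds ratio is read at 0.05, the chance of at least one false positive is about 9% to 12%, depending on the contrasts. This rests on three equal arms, independent subjects and a 5% level that the documents never state. With multi-person clusters and no allowance for them, the figure would be higher. A joint test first brings it to 5% or less, provided that there are three arms and the model accounts for the clusters.

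**What to change.** In Data Analysis:

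1. Change clusters to arms in the balance sentence, so that it agrees with the later one. Describe baseline per arm. If a test is kept for continuous measures, use a three-arm method: a linear model with a three-level arm factor, or Kruskal-Wallis.
2. Drop the rule that adjusts for whatever differs. Name the covariates in advance from the baseline variables that the section already lists, for example age, gender, baseline intent to start home dialysis, and current nephrologist care. Leave out the engagement measure and other items in that list that are observed after randomisation. Per-arm description alone is not enough, because it would leave the present covariate rule with no trigger.
3. Enter arm as one three-level factor in a logistic model that accounts for the randomised clusters, for example through cluster-robust standard errors or a random cluster effect. Read the joint 2-df test first, and interpret pairwise odds ratios as findings only if it is below 0.05. Label the June 2022 comparison supportive.
4. Reconcile the arm count across the background and Study Design and Procedures. If it proves to be four, the joint-test argument no longer suffices and a multiplicity rule for four arms is needed.

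The cost is wording, with no new data. The price is a somewhat lower chance of at least one significant contrast, as in the example above. Pairwise 95% intervals would still be unadjusted and should be described as such.
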